### **2.5 DATA HANDLING CONVENTIONS**

This section describes general rules for data handling conventions, especially for patients with missing data.

#### **2.5.1 General conventions**

The following formulas will be used for computation of parameters.

##### ***Reference day***

The reference day for the calculation of extent of exposure, time to onset and relative days is the day of the first administration of open-label IMP, denoted as Day 1.

##### ***Disease characteristics formulas***

Duration of diabetes (years) = (Date of informed consent – date of diagnosis of diabetes +1)/365.25.

Age at onset of diabetes (years) = (Date [DD-MM-YYYY] of diagnosis of diabetes – date [DD-MM-YYYY] of birth +1) /365.25. In case of unavailable date of birth, only the year of the

date of diabetes diagnosis and the year of the date of birth (retrieve using the age recorded at screening) will be considered in the age at onset calculation.

Duration of previous mealtime insulin treatment (years) = (Date of informed consent – Date of first intake of mealtime Anti-hyperglycemic therapy +1)/365.25.

Duration of basal insulin treatment (years) = (Date of informed consent – Date of first intake of Basal Anti-hyperglycemic therapy +1)/365.25

### ***Renal function formula***

GFR will be derived using MDRD formula:

$$\text{GFR (mL/min/1.73m}^2\text{)} = \left[ 175 \times \text{Serum Creatinine (mg/dL)}^{-1.154} \times \text{Age}^{-0.203} \times 1.212 \text{ (if black)} \right. \\ \left. \times 0.742 \text{ (if female)} \right]$$

## **2.5.2 Missing data**

### ***2.5.2.1 Handling of missing PK parameters***

For participants with insufficient data for some but not all PK parameters, the evaluable PK parameters will be included in the analysis. No imputations of missing PK parameters are planned.

### ***2.5.2.2 Handling of other missing parameters***

For categorical variables, patients with missing data are not included in calculations of percentages unless otherwise specified. When relevant, the number of patients with missing data is presented.

Derived variables are considered missing if the original variables required to calculate them are missing unless otherwise specified. For example, if either a baseline assessment or an endpoint assessment is missing for a particular patient, then the change from baseline at endpoint is missing. Depending upon the assessment, analyses may not include all patients in the analysis population, because certain patients in the intended population may have missing data.

### ***Handling of computation of treatment duration if investigational medicinal product end of treatment date is missing***

For the calculation of the treatment duration, the date of the last dose of IMP will be defined as the date of last administration reported on the end-of-treatment case report form page. If this date is missing, the exposure duration should be left as missing.

The last dose intake should be clearly identified in the case report form and should not be approximated by the last returned package date.

### ***Handling of medication missing/partial dates***

No imputation of medication start/end dates or times will be performed. If a medication date or time is missing or partially missing and it cannot be determined whether it was taken prior or concomitantly, it will be considered a prior, concomitant, and posttreatment medication.

### ***Handling of adverse events/hypoglycemia with missing or partial date/time of onset***

Missing or partial adverse event / hypoglycemia onset dates and times will be imputed so that if the partial event onset date/time information does not indicate that the event started prior to treatment or after the on-treatment period, the event will be classified as treatment-emergent. No imputation of event end dates/times will be performed. These data imputations are for categorization purpose only and will not be used in listings. No imputation is planned for date/time of event resolution.

### ***Handling of adverse events/ hypoglycemia when date and time of first IMP administration is missing***

When the date and time of the first IMP administration is missing, all adverse events/ hypoglycemia that occurred on or after the day of randomization should be considered as treatment-emergent. The exposure duration should be kept as missing.

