### 2.3.2 Safety population

The safety population is defined as all randomized patients who receive at least one dose of IMP, analyzed according to the treatment actually received.

In addition:

- If a patient is dispensed IMP and is lost to follow-up without any documented evidence whether or not the patient took IMP, the patient will be considered exposed and included in the safety population.
- Randomized patients for whom it is unclear whether they took the study medication will be included in the safety population as randomized.
- Non randomized but treated patients will not be part of the safety population, but their safety data will be presented separately.

- Randomized patients having taken at least one kit of SAR341402 will be considered in the switching arm. Patients randomized in the switching arm but having taken only Novolog as treatment will be considered in the non-switching arm.

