### ***Duration of exposure***

The duration of exposure will be the total number of days of administration of the open-label IMP, ignoring temporary drug discontinuation (see [Section 2.5.1](#) for calculation in case of missing or incomplete data).

The duration of exposure to the open-label IMP will be defined in days as:

(Date of the last IMP administration – date of the first IMP administration) + 1

The process described in [Section 2.5.1](#) will be applied to define the date of the last IMP administration. If this date is missing, the IMP exposure duration should be left as missing.

Duration of IMP exposure will be summarized descriptively as a quantitative variable (number, mean, SD, median, minimum, and maximum). The number (n) and proportion (%) of patients exposed to the open-label IMP will be presented by specific time periods for each treatment group in the safety population.

The time periods of interest are grouped as follows:

- Up to 4 weeks,
- >4 to 8 weeks,
- >8 to 12 weeks,
- >12 to 15 weeks,
- >15 to 16 weeks,
- >16 to 24 week,
- >24 weeks.

The cumulative duration of exposure will be described using the following time periods:

- $\geq$  1 day,
- >4 weeks,
- >8 weeks,
- >12 weeks,
- >15 weeks,
- >16 weeks,
- >24 weeks.

Additionally, the cumulative duration of treatment exposure will be provided, defined as the sum of the duration of treatment exposure for all patients, and will be expressed in patient-years.

If the number of patients impacted by COVID-19 is sufficient, the duration of IMP exposure will also be presented by subgroup of COVID-19 impact (Non-impacted, Impacted) (see definition [Section 2.2](#)).

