### ***Daily insulin doses***

All insulin doses will be reported by patient in e-diary, transferred to the IMP/NIMP e-diary page of the eCRF and reviewed by the investigator in dedicated items. In case the insulin doses reported by the patient are incorrect, the investigator will invalidate them and enter correct doses in the IMP/NIMP back-up e-diary page of the eCRF. For the analyses, the investigator entries will prevail when compared from the transferred e-diary data.

The process described in [Section 2.5.3](#) will be applied to assign visits to the insulin doses transferred from the e-diary webportal into the clinical database, and to retrieve doses in case of premature treatment discontinuation.

At baseline, the daily basal, mealtime, and total (basal plus mealtime) insulin doses (U and U/kg body weight) will be calculated as follows:

- Daily basal insulin dose at baseline (U and U/kg) = median of daily basal insulin doses available up to 7 days before the day of first IMP,
- Daily mealtime insulin dose at baseline (U and U/kg) = median of daily mealtime insulin doses available up to 7 days before the day of first IMP,
- Daily total insulin dose at baseline (U and U/kg) = median of daily total insulin doses available up to 7 days before the day of first IMP.

At Visit 3, daily insulin doses (basal, mealtime, and total) will be calculated as the median of daily insulin doses available in the week after the day of first IMP. At further visits, the daily insulin doses (basal, mealtime, and total) will be calculated as the median of daily insulin doses available in the week before the visit. Technical details related to the computation and handling of missing data are described in [Section 2.5](#).

The daily insulin doses (basal, mealtime, total) will be described at baseline, during the week after the date of the first IMP administration, then at each visit, and the changes from baseline will be presented. Figures will be provided.

The ratio of the daily basal insulin/total insulin dose observed and change from baseline will be described at baseline and at each visit.

The daily insulin doses (basal, mealtime, total) will be summarized according to categories of HbA1c change from baseline to Week 16 (<-1%, ≥-1% to ≤1%, >1%).

If the number of patients impacted by COVID-19 is sufficient, daily insulin doses will also be presented by subgroup of COVID-19 impact (Non-impacted, Impacted) (see definition [Section 2.2](#)).

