#### ***Number and rate of hypoglycemia per patient-year***

- Number and rate of hypoglycemia per patient-year (computed as  $365.25 \times [\text{total number of episodes of hypoglycemia}] / [\text{total number of days exposed}]$ ) will be summarized by treatment group for any hypoglycemia and for each hypoglycemia category (as described in [Section 2.1.5.1](#)). Non classified hypoglycemia will be displayed.
- For any hypoglycemia the cumulative mean number of hypoglycemia per patient will be summarized over time using Nelson-Aalen estimates. Figures will be provided.
- For any hypoglycemia, severe and documented symptomatic hypoglycemia category, number and rate of hypoglycemia per patient-year will be compared for the switching arm versus the non-switching arm using an overdispersed Poisson regression model with a log-link function, and the logarithm of the treatment-emergent period as offset (using PROC GENMOD). The dispersion parameter will be estimated by Pearson's chi-square statistic divided by its degrees of freedom (option SCALE=PEARSON). The model will include fixed-effect terms for treatment group and the randomization stratum of screening HbA1c ( $<8\%$ ,  $\geq 8\%$ ). If a model does not converge (eg, due to sparse data), the randomization stratum may be removed from the model. Rate ratios and 95% CIs will be displayed using forest plots.
- The number of severe hypoglycemia with neuroglycopenic symptoms and/or SMPG  $<2.8$  mmol/L (50 mg/dL) per patient-year of exposure will be summarized by treatment group.

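### When the first IMP date is missing, the SAP counts a participant's hypoglycemia episodes in the crude rate but gives that participant no exposure days

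*SAP*

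**What the plan says.** - **Events and exposure, first IMP date and time missing** (SAP 2.5.2.2): two consecutive sentences rule that adverse events and "hypoglycemia that occurred on or after the day of randomization should be considered as treatment-emergent. The exposure duration should be kept as missing".
- **Exposure, last IMP date missing**: SAP 2.4.3.1 (Duration of exposure) says "If this date is missing, the IMP exposure duration should be left as missing", and 2.5.2.2 repeats the rule: "If this date is missing, the exposure duration should be left as missing". Neither place says how dated episodes are then classified.
- **Exposure formula** (SAP 2.4.3.1): last IMP date minus first IMP date, plus one. Both dates are needed.
- **Crude rate** (SAP 2.4.5.1; also Protocol Table 7): 365.25 times episodes divided by days exposed. The SAP takes group totals over on-treatment events in the safety population. Nothing there removes the episodes of participants whose exposure is missing.
- **Poisson model** (SAP 2.4.5.1): it uses "the logarithm of the treatment-emergent period as offset". The SAP does not define that period under that name. The on-treatment period in 2.1.5 runs from first injection to last injection plus one day.

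**The concern.** A rate needs the same people above and below the line. Here the numerator rule and the denominator rule for one participant stand in consecutive sentences and point in different directions: the episodes are kept and the days are not. The error has one direction only, because the crude rate can rise or stay the same but cannot fall.

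The number of hypoglycemic events per participant-year is a named secondary safety endpoint (Protocol Section 3). If the affected participants sit mainly in one arm, the comparison of tabulated rates shifts by the same factor. The tabulated rates may then disagree with the modeled rate ratio for a reason unrelated to treatment.

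**Working it through.** The documents state no figure for this point, so there is none to reproduce.

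**Inputs**
- n = 92 per arm: 184 planned, 1:1 (SAP 1.3), 184/2 = 92. The safety population may differ slightly.
- Planned treatment: 16 weeks = 112 days (SAP 1.4).
- k, the number in an arm with missing exposure whose episodes still count: not given; assumed 1 to 5.
- f, their true follow-up as a fraction of the others' mean: not given; assumed 0.25, 0.5 or 1.

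**Formula.** Let everyone have episode rate λ, and let those with dates have mean time T.
- Episodes counted: λ[(n−k)T + k·f·T]
- Days counted: (n−k)T
- Tabulated rate / true rate = 1 + k·f/(n−k)

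**Results, n = 92**

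| k | f = 1 | f = 0.5 | f = 0.25 |
|---|---|---|---|
| 1 | 1/91 = +1.1% | +0.5% | +0.3% |
| 2 | 2/90 = +2.2% | +1.1% | +0.6% |
| 3 | 3/89 = +3.4% | +1.7% | +0.8% |
| 5 | 5/87 = +5.7% | +2.9% | +1.4% |

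The inflation is zero if the affected participants have no recorded episodes. With equal k and f in equal-sized arms it cancels in the rate ratio, but each arm's rate stays too high.

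**Simulation check.** 500 trials were run with 92 per arm, 112 days, overdispersed counts at an assumed 60 episodes per patient-year in both arms, and five missing exposures in one arm. The Poisson model used a Pearson scale and dropped records without an offset; that dropping is an assumption about software, not an SAP rule.
- Affected arm's crude rate: 63.8 with the mismatch, 60.4 when numerator and denominator use the same people.
- Mean ratio of tabulated rates: 1.073. Mean model rate ratio: 1.014. Both carry a small upward bias from averaging ratios.
- 1.073/1.014 = 1.058, which agrees with the algebra (1 + 5/87 = 1.057).

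**Time base.** Even with complete dates, the table divides by days exposed (112). If the offset is the on-treatment period, the model uses 113 days. 113/112 = 1.009, a 0.9% difference in the rate that cancels in the rate ratio when durations are similar.

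**The case against.** **The general missing-data rule may already exclude these participants.** SAP 2.5.2.2 treats a derived variable as missing when its inputs are missing, and accepts that analyses may omit patients with missing data. This stands as a possible reading, and it is why the overstatement is conditional. It does not settle the matter. The rule does not name this rate, the rate is a ratio of group totals rather than a per-patient variable, and the more specific rule expressly keeps the episodes. Two programmers could produce different tables.

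**The effect is hypothetical and small.** This stands. No count is given, the SAP wants the last dose clearly identified in the CRF, and the f = 1 cases need a fully followed participant with no first-dose date. Safety analyses are descriptive, and the protocol calls the rate ratios exploratory.

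**Leaving exposure missing looks deliberate.** The SAP refuses the last returned package as a proxy for the last dose and favors calling uncertain events treatment-emergent. That is reasonable for incidence tables. It does not justify a rate whose numerator and denominator cover different people.

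**Readings that go too far**
- *A missing last date has the same effect by rule.* The documents write only the missing exposure. The neighboring rule on incomplete onset dates concerns the event's date, not the last IMP date. This is a gap, not a stated mismatch.
- *The SAP drops these participants from the Poisson model.* It does not say so. The offset is the treatment-emergent period, not exposure duration, and the day of randomization used for events could serve as its start if the last date is known.
- *The lost-to-follow-up rule in SAP 2.3.2 supplies the cases, and the e-diary recovers them.* That rule says "the patient will be considered exposed and included in the safety population", but only where there is no documented evidence either way on IMP intake. The SAP also states "All insulin doses will be reported by patient in e-diary, transferred to the IMP/NIMP e-diary page of the eCRF". Someone with diary IMP doses therefore has such evidence, and someone truly in the group has no doses to recover and probably few recorded episodes.

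**Conclusion.** The point holds for a missing first IMP date. As written, the rules keep the episodes and omit the days, so the arm's crude rate per patient-year would be overstated if any such participant has recorded episodes. The size is about 1.1% of one arm's rate per fully followed participant of 92, and less for shorter follow-up. This rests on assumed k and f and on a common episode rate.

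Whether the table and the Poisson model use the same participants is left open, as is the classification of episodes when the last IMP date is missing. A reader might infer that the reported rates are in fact inflated, or that table and model must disagree; the documents support neither as a certainty. The incidence tables and the primary PK analysis are unaffected. This is a minor correction to a stated rule.

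**What to change.** In SAP 2.5.2.2 and 2.4.5.1:

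1. State that the crude rate and the Poisson model use the same participants and the same time base, and name that time base.
2. If the first IMP date is missing, start the rate denominator and the offset at the first IMP dose recorded in the e-diary, or at the day of randomization, which 2.5.2.2 already uses for events. Choose one, and count episodes for the rate from the same day.
3. If the time at risk still cannot be determined, including when the last IMP date is missing, leave the participant out of both numerator and denominator of the rate and out of the model. Keep them in the incidence tables, and report how many participants and episodes were left out.

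The last e-diary dose should not be made a required end of the on-treatment period. If diary entry stops before dosing does, it would shorten exposure and push later episodes into the post-treatment period.

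The cost is a few sentences and one derivation rule before database lock. The downside is that a few episodes may be left out of the rate, which the reported count makes visible.

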### ***Handling of hypoglycemia classification when some classification items are missing***

Rules for handling missing data in classification items for hypoglycemia will be provided in ADaM metadata.

### ***Handling of missing assessment of relationship of adverse events to investigational medicinal product***

If the assessment of the relationship to IMP is missing, then the relationship to IMP has to be assumed and the adverse event considered as such in the frequency tables of possibly related adverse events, but no imputation should be done at the data level.

### ***Handling of potentially clinically significant abnormalities***

If a patient has a missing baseline he will be grouped in the category “normal/missing at baseline.”

For PCSAs with 2 conditions, one based on a change from baseline value or a normal range and the other on a threshold value, with the first condition being missing, the PCSA will be based only on the second condition.

For a PCSA defined on a threshold and/or a normal range, this PCSA will be derived using this threshold if the normal range is missing; eg, for eosinophils the PCSA is  $> 0.5$  GIGA/L or  $> \text{ULN}$  if  $\text{ULN} \geq 0.5$  GIGA/L. When ULN is missing, the value 0.5 should be used.

Measurements flagged as invalid by the laboratory will not be summarized or taken into account in the computation of PCSA values.

### ***Handling of missing data in the calculation of insulin doses***

The daily mealtime insulin dose will be calculated as the sum of the mealtime insulin doses collected on the same day. At least 3 available mealtime insulin doses for the main meal (breakfast, lunch and dinner) and no more than 1 snack will be required to calculate the daily mealtime insulin dose. For the days with more than one snack or more than one main meal with an insulin dose of 0 unit, the daily dose won't be calculated.

The daily total insulin dose will be calculated as the sum of the daily basal (only the doses not null will be kept) and daily mealtime insulin doses. If one of the daily insulin doses is missing (basal or mealtime), the daily total insulin dose will not be calculated.

At baseline, daily insulin doses (basal, mealtime, and total) will be calculated as the median of the daily insulin doses (as previously calculated) available in the 7 days before the day of first IMP. At Visit 3, daily insulin doses (basal, mealtime, and total) will be calculated as the median of the daily insulin doses (as previously calculated) available in the 7 days after the day of first IMP. At further visits, the daily insulin doses (basal, mealtime, and total) will be calculated as the median of the daily insulin doses (as previously calculated) available in the 7 days before the visit. No minimum number of available doses will be required. For insulin doses in U/kg, if the body weight measurement is missing at a given visit, the last available measurement from previous visit (unscheduled or not) will be used.

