### 6.5.1 Evaluation of participants not meeting glycemic goals

- In case of SMPG not meeting the target in spite of successive insulin dose titration, the Investigator should ensure and document that no reasonable explanation exists for insufficient glucose control and in particular that:
  - Fasting plasma glucose was actually measured in fasting condition (ie, after at least 8 hours fasting),
  - Rebound hyperglycemia is excluded,
  - IMP/NIMP doses are properly adjusted,
  - Correction doses for pre-prandial glucose values above goal are used by participant,
  - There is no inter-current disease which may jeopardize glycemic control (eg, infectious disease),
  - Compliance to diet and lifestyle is appropriate, in particular, dosage adjustment for changes in meal content and SMPG.
- If any of the above can reasonably explain the insufficient glycemic control, the Investigator should undertake appropriate action, eg:
  - Further titrate the IMP/NIMP, if deemed safe by the Investigator,
  - Set up adequate investigation and treatment of inter-current disease (to be reported in AE/SAE/concomitant medication parts of the eCRF),
  - Stress the absolute need to be compliant to treatment,
  - Stress the importance of consistency in meals and insulin dosing, particularly during this time of poor glycemic control,
  - Monitor night time glucose,
  - If deemed appropriate, organize a specific interview with a Registered Dietician or other medically qualified person to stress on the absolute need to be compliant to diet and lifestyle recommendations, in particular with attention to awareness of the meal content and covering all snacks with a dose of rapid-acting insulin.

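### SAP 2.5.2.2 leaves fully recorded days with more than one snack out of the daily mealtime and total insulin dose, which can understate dose in frequent snackers and mute change when snack dosing changes

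*SAP*

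**What the plan says.** SAP 2.5.2.2, under the handling of missing data in insulin doses, builds the visit value in steps.

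- **Definition:** "The daily mealtime insulin dose will be calculated as the sum of the mealtime insulin doses collected on the same day".
- **Eligibility of a day:** "At least 3 available mealtime insulin doses for the main meal (breakfast, lunch and dinner) and no more than 1 snack will be required" before that sum is formed.
- **Exclusion, stated again:** "For the days with more than one snack or more than one main meal with an insulin dose of 0 unit", no daily dose is computed.
- **Total dose:** "If one of the daily insulin doses is missing (basal or mealtime), the daily total insulin dose will not be calculated".
- **Visit value:** after Visit 3 it is "calculated as the median of the daily insulin doses (as previously calculated) available in the 7 days before the visit". Baseline uses the 7 days before first IMP, and Visit 3 the 7 days after it. "No minimum number of available doses will be required".

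No reason is given for the snack limit. SAP 2.4.3.1 separately provides for diary doses that are wrong: "the investigator will invalidate them and enter correct doses in the IMP/NIMP back-up e-diary page of the eCRF".

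Change in basal, mealtime and total dose from baseline to Week 16 is a tertiary/exploratory endpoint (Protocol Table 2). Protocol 3.1 says that HbA1c and dose changes will help in judging the clinical relevance of treatment-emergent antibodies and of PK outliers. SAP 2.4.6.1 and 2.4.6.2 accordingly tabulate and plot dose change against AIA and NAb results.

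**The concern.** The rule sits under missing data, but a day with three main-meal doses and two snack doses is a complete record. Leaving it out contradicts the SAP's own definition of the daily dose as a sum. The exclusion also depends on the quantity being measured: if snack doses come on top of meal doses, the excluded days are the higher-dose ones. With no minimum number of days, a single unrepresentative day can stand for the week. If every recorded day has more than one snack, the participant has no mealtime or total dose at that visit.

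At stake is the reading of mealtime and total dose as supportive evidence on antibodies. If part of a greater insulin need appears as additional snack injections, the rule moves those days from higher dose to not calculated, and the recorded change shrinks.

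**Working it through.** The documents attach no figure to this rule and give no snack frequency or snack dose, so there is no stated number to reproduce. The inputs below are assumptions, chosen only to show direction and scale: main meals 8 + 8 + 8 = 24 U a day, 2 to 4 U per snack dose added on top, and a Poisson number of snack doses a day with mean m.

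**1. One week, 2 U per snack.** Three days with 1 snack (26 U), two with 2 (28 U), two with 3 (30 U).
- All days kept: 26, 26, 26, 28, 28, 30, 30; median 28 U.
- SAP rule: the last four days are dropped; median of 26, 26, 26 is 26 U.

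**2. Mean daily dose in closed form, 3 U per snack.** The share of days dropped is 1 − (1 + m)e^(−m). The mean over all days is 24 + 3m. Given at most one snack, the expected number of snacks is m/(1 + m), so the mean over kept days is 24 + 3m/(1 + m).

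| m | Days dropped | All days (U) | Kept days (U) |
|---|---|---|---|
| 0.5 | 9% | 25.5 | 25.0 |
| 1 | 26% | 27.0 | 25.5 |
| 1.5 | 44% | 28.5 | 25.8 |
| 2 | 59% | 30.0 | 26.0 |

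**3. The SAP's own statistic, the median of available days.** This was simulated for 100,000 participants with 7 diary days each and a 15% day-to-day SD on the main-meal total. The understatement is among participants with a value, over 2 to 4 U per snack:

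| m | Understatement | No visit value |
|---|---|---|
| 0.5 | 1–2% | 0% |
| 1 | 4–6% | 0.01% |
| 1.5 | 6–11% | 0.3% |
| 2 | 9–15% | 2.6% |
| 3 | 14–23% | 21% |

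**4. Missing visit values.** If p is the chance that a day has more than one snack, independently across days, all 7 days are lost with probability p^7: 0.8% at p = 0.5, 8.2% at 0.7, 21% at 0.8, 48% at 0.9. With only 3 diary days it is p^3: 12.5%, 34%, 51% and 73%.

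**5. Change from baseline in the weekly median, 3 U per snack.**

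| Snack doses a day, baseline to Week 16 | All days (U) | SAP rule (U) |
|---|---|---|
| 1 to 1 | −0.02 | −0.01 |
| 1 to 1.5 | +1.46 | +0.32 |
| 1.5 to 1 | −1.44 | −0.31 |

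The closed form in step 2 agrees for the middle row: 28.5 − 27.0 = +1.5 U with all days, 25.8 − 25.5 = +0.3 U under the rule.

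**6. Stable snacking, every dose raised by 20%.** At m = 1: 0.2 × 27.0 = 5.4 U over all days, against 0.2 × 25.5 = 5.1 U under the rule. At m = 2: 0.2 × 30.0 = 6.0 U against 0.2 × 26.0 = 5.2 U. The relative change is 20% in each case.

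**The case against.** The strongest defence is that the endpoint is a change from baseline, compared between randomised arms under one rule applied at every visit. A lower level need not distort that change. Steps 5 and 6 bear this out: with steady snacking the change is nearly right, and a general titration of doses still shows. Protocol Table 3 describes titrating mealtime doses to glucose targets, not adding snack injections. This part stands and confines the problem to changing or unequal snack dosing.

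The second defence is textual. In "For the days with more than one snack or more than one main meal with an insulin dose of 0 unit", the zero-unit phrase may qualify snacks as well as main meals, so that only zero-dose snacks would trigger exclusion. The preceding sentence, however, sets the one-snack limit with no such qualifier. The plain reading therefore excludes days with two dosed snacks, and programmers could implement either version.

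Stronger readings are tempting, but the documents do not support them:

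- *The protocol tells participants to cover all snacks, so compliant participants are dropped.* The phrase "covering all snacks with a dose of rapid-acting insulin" is in Protocol 6.5.1. It concerns participants missing SMPG targets despite titration, and belongs to an optional dietary interview. It is not a general instruction.
- *Correction doses cause exclusion too.* The SAP names only snacks and zero-unit main meals, and the documents do not say how corrections are recorded.
- *Insulin dose is the main signal of an antibody effect.* Protocol 3.1 names it together with HbA1c and calls the efficacy data supportive only. SAP 2.4.6.1 also examines hypoglycemia and reactions.

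**Conclusion.** The point holds as a defect in a derivation rule. On its plain reading, SAP 2.5.2.2 drops complete days without a stated reason and against its own definition. Where snack doses are additive, it understates mealtime and total dose in frequent snackers. In the illustration this is roughly 4–6% at one snack dose a day and 9–15% at two. A missing visit value is rare unless more than one snack is the habit on most days or few diary days exist.

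A reader might infer that the rule removes the increase the endpoint is meant to detect. That goes too far. It attenuates the part of a change that comes from the number of snack doses (about +0.3 U shown for +1.5 U in the example) and leaves a proportional change in all doses intact. Bias between arms needs snack dosing to differ by arm. The trial is open-label, so that cannot be ruled out, but the documents give no evidence for it.

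All sizes rest on assumed snack frequency, snack dose and additivity, with the same mean snack rate for everyone. The endpoint is tertiary and descriptive. Basal dose and the primary and secondary endpoints are untouched.

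**What to change.** In SAP 2.5.2.2:

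1. Delete the limit of one snack. Define the daily mealtime dose as the sum of all recorded mealtime and snack doses on days with an entry for each main meal; the total dose follows.
2. State whether the zero-unit clause applies to main meals only.
3. Send implausible entries through the investigator correction step already in SAP 2.4.3.1 instead of excluding the day.
4. Report the number of days contributing to each visit value, by visit and arm.

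If the sponsor has a reason to keep the limit, it should state it and show the all-doses version as a sensitivity summary.

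The cost is a wording change, slightly more programming and possibly a few more diary queries. No new data are needed.
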